In Europe, cochlear implantation has become an accepted treatment for patients with UHL. The majority of literature regarding patients with UHL and cochlear implantation involves adults. It has been reported as a viable treatment option in cases of UHL, including sudden sensorineural hearing loss (Firszt et al, 2012), and severe tinnitus (Vermiere & Van de Heyning, 2009; Van de Heyning et al, 2008). Further, cochlear implantation has been shown to offer superior speech perception in noise, sound localization abilities, and subjective perception of hearing quality compared to CROS hearing aids and bone-conduction devices (Arndt et al, 2011).

The practice of providing cochlear implants to children who have significant hearing loss in one ear is of great interest and is occurring with greater frequency as reported in case studies and small set clinical reports (Gantz, et al. 2000, Cadieux et al., 2013; Hassepass, et al., 2013; Plontke et al., 2013; Tzifa and Hanvey, 2013; Távora-Vieirea and Rajan, 2015; Arndt, et al, 2015). Children with severe to profound UHL may have greater potential to benefit from cochlear implantation than adults with UHL from a developmental point of view due to their neural plasticity. They may be more amenable to gaining binaural listening skills after cochlear implantation.

The primary goal of this project is to determine whether children with UHL experience an improvement in speech perception, hearing in noise, localization, and quality of life with a cochlear implant as compared to an unaided listening condition.

2) Objective

The primary purpose of this feasibility study is to demonstrate the effectiveness of cochlear implantation in children with moderate to profound UHL. Postoperative results will be evaluated with:

- i) speech perception measures,
- ii) localization tasks,
- iii) hearing in noise tasks,
- iv) subjective reports.

3) Definitions

Adjusted Constant Error: the rms deviation of the mean responses from the diagonal, computed after compensating for bias. This procedure reduces the bias

when evaluating the relationship between the average response on the azimuth and signal source on the azimuth.

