 - (b) Hearing thresholds in the contralateral ear of ≤ 25 dB HL
 - (2) Between 3 years, 6 mos and 6 years, 6 mos of age at implantation.
 - (3) Anatomically normal cochlear nerve
 - (4) Cochlear anatomy that is amenable to cochlear implantation as evaluated by imaging (modality at the physician's discretion) including:
 - (a) Normal cochlear anatomy or

- (b) Incomplete Partition Type II (IP2) with or without Enlarged Vestibular Aqueduct (EVA) or
- (c) EVA with normal partitioning
- (5) No evidence of progressive hearing loss.
- (6) Willing to undergo 4 week hearing aid trial as warranted based on achieving desired audibility when fitted via real ear DSL method. See Reference Appendix B.
- (7) Aided word recognition in the ear to be implanted of 30% or less as measured with CNC words (50-word list)
 - (a) When listening with an appropriately fit hearing aid and masking applied to the contralateral ear (Turner, 2004).
 - (b) Aided testing will be conducted in a sound-proof booth with the participant seated 1 meter from the sound source, facing 0° azimuth. Recorded materials will be presented at 60 dB SPL.
 - (c) The hearing aid output will be measured using DSL targets.
- (8) Realistic parental expectations: *a verbal acknowledgement of the potential benefits and risks, and postoperative variation in performance. For instance, cochlear implantation will not restore normal hearing.*
- (9) Willing to obtain recommended meningitis vaccinations per CDC recommendations.
- (9) Development and cognition within the normal range as measured by the Leiter-R test of nonverbal intelligence and cognitive abilities.
- (10) Parental commitment to study parameters including being able and willing to participate in evaluation schedule, involvement in prescribed therapy, and travel to investigational site and study-related activities.

ii) Exclusion Criteria

- (1) English is not primary language of the home
 - (a) Speech perception materials are presented in English
 - (b) Parental questionnaires are administered in English
- (2) Conductive hearing loss in either ear
- (3) Compromised auditory nerve
- (4) Ossification of the cochlea
- (5) Inability to participate in follow-up procedures (i.e., unwillingness, geographic location)
- (6) History of condition that contraindicates middle or inner ear surgery or anesthesia (i.e. otitis media refractory to treatment)
- (7) Case of sudden sensorineural hearing loss that has not been first evaluated by a physician

iii) Enrollment

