- (1) Speech, Spatial and Qualities of Hearing Scale (SSQ), (Gatehouse & Noble, 2004). The SSQ questionnaire assesses performance in three domains, hearing speech in quiet and noise environments (9 items), spatial or directional hearing (5 items) and sound qualities (8 items), which address sound segregation and listening effort. Each item is rated on a 10-point scale. Domain scores represent an average of item ratings. A modified version of this test will be used.
- (2) Bern SSD Questionnaire, (Kompis, Pfiffner, Krebs & Caversaccio , 2011). This is a 10-item questionnaire used for rating the subjectively perceived benefit of a hearing technology designed to be used for persons with UHL. A modified version of this test that can be completed by a parent will be used.
- (3) PedsQL Multidimensional fatigue scale (Varni, Limbers & Burwinkle, 2007). This is a validated scale for determining fatigue in young children, including general fatigue, sleep/rest fatigue and cognitive fatigue. Scores from this test have been previously demonstrated to be substantially affected by hearing loss in children (Hornsby et al 2013).

e) Aural Rehabilitation

- i) Participants and their parents will participate in aural rehabilitation sessions with a board-certified speech-language pathologist
- ii) Sessions will occur either in person or via tele-therapy at the time of the initial stimulation, 2-week follow up, 5 week follow up, and twice a month following for the first 6 months after the initial stimulation. Sessions will continue once per month for the next 6 months until the first annual follow up.
- (a) The option to continue on a once per month basis for the second year following the initial stimulation will be offered but will not be required.

7) Proposed Claims

- a) Demonstrate the effectiveness of cochlear implantation in children with moderate to profound UHL
 - i) Demonstrate an improvement in speech perception abilities, localization, and/or subjective benefit in an aided (cochlear implant on) versus an unaided (cochlear implant off) condition

- ii) Demonstrate improvement in ability, or improved ease, to participate in natural environments based on parental perception of benefit.

8) Statistical Analysis

- a) Descriptive summaries will be provided for the following: participant demographics, and frequency of major and minor complications/adverse events.

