- b) A single-subject design will be utilized, where each participant serves as his or her own control, for analysis of objective and subjective results. A single-subject design was chosen in order to accommodate the heterogeneity that is well known to characterize auditory prosthesis research. Repeated-measures ANOVA will be calculated with a p-value of ≤ 0.05 for statistical significance. Statistical analysis will be conducted with SPSS software.
 - i) Comparison of aided speech perception performance to the baseline condition (either unaided or aided with hearing aid, depending on the participants residual hearing) and in the post-initial activation intervals to evaluate trends over time
 - ii) Comparison of localization abilities to the baseline condition (either unaided or aided with hearing aid, depending on the participant's residual hearing) and in the post-initial activation intervals to evaluate trends over time
 - iii) Compute the overall rms error, random error, constant error, and adjusted constant error, as described by Grantham et al (2007)
 - iv) Comparison of subjective report scores in the post-initial activation intervals. Group means compared with Bonferroni's adjusted t tests or repeated-measure ANOVAs. Pearson's correlations will be used to analyze relationships between variables.
 - v) Subjective report scores will be compared to norms for this test. Group means compared with Bonferroni's adjusted t tests or repeated-measure ANOVAs. Pearson's correlations will be used to analyze relationships between variables.
- c) The incidence of interference between ears will be assessed at the 6,12 and 24 month post initial stimulation visit by comparing the speech perception performance in the 0° azimuth conditions for the contralateral ear only versus cochlear implant + contralateral ear conditions for each participant, as well as the individual's subjective report.

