A sample size of 20 participants was selected due to known variability in conventional cochlear implant recipient outcomes and to allow for possible dropouts (approximately 20%). A comparable study, Hansen, Gantz & Dunn (2013) evaluated 29 adult cochlear implant participants with UHL, which included etiologies of sudden sensorineural hearing loss, Meniere's disease, and vestibular schwannoma. Authors reported a high degree of variability in their sample. This project will not enroll all of the etiologies included in the Hansen, Gantz & Dunn (2013) analysis (such as, Meniere's Disease with intractable vertigo or history of vestibular schwannoma), therefore a smaller sample size was selected. The inclusion/exclusion criteria associated with this study, as compared to the heterogeneity of the Hansen, Gantz, & Dunn (2013) subject sample, will allow for more generalized comments about subjective and objective outcomes of cochlear implantation in pediatric cases of UHL.

If needed, statistical consultation will be sought from the North Carolina Translational and Clinical Sciences Institute (TraCS) or UNC Odum Institute.

9) Endpoints

- a) Safety endpoint
 - i) The primary safety endpoint is the evaluation of Adverse Events. All Adverse Events will be reported to the UNC IRB. If the UNC IRB or study investigators deem an Adverse Event unacceptable, then this would result in termination of the study.
- b) Primary effectiveness endpoint
 - i) The primary effectiveness endpoint is the comparison of speech perception, localization abilities and/or subjective report when the cochlear implant is on versus the preoperative unaided condition as well as changes in quality of life as measured by the Speech, Spatial and Qualities of Hearing Scale (SSQ), (Gatehouse & Noble 2004), the modified Bern SSD Questionnaire, (Kompis, Pfiffner, Krebs & Caversaccio , 2011) and the PedsQL Multidimensional fatigue scale (Varni, Limbers & Burwinkle, 2007).

10) Risk Analysis

- a) Potential risks to cochlear implantation

The following are risks associated with the MED-EL Synchrony implant, which is included in the device description:

1. Loss of residual hearing
2. Dizziness
3. Increased vertigo
4. Delay of healing of the scar
5. Impairment of the sense of taste

6. Potential for swallowing difficulties
7. Numbness
8. Increased tinnitus
9. Stimulation of the facial nerve
10. Temporary pain and uncomfortable sounds during stimulation

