complete a hearing aid trial prior to enrollment to evaluate outcomes with conventional amplification. If a child has any residual hearing in the ear to be implanted, surgical placement of a cochlear implant will result in a loss of this hearing. The amount of functional gain a hearing aid can afford for a hearing loss with a pure tone average of >70dB HL will be very likely be insufficient to achieve comprehension of spoken language. Current research in performance outcomes for children with cochlear implants suggests that children with a 67dB PTA have a 80% chance of improved hearing with a cochlear implant and children with a 73dB PTA have a 85% chance of improvement with a cochlear implant (Leigh, Dettman & Dowell, 2016). If a child does not benefit from the cochlear implant, or does not elect to use it, this does not preclude him or her from use of a CROS hearing aid or Bone Conduction device in the future. This technology, which uses a contralateral microphone to route sound to the better hearing ear, either by way of short wave radio or bone conduction, can still be used.

- (1) The test battery includes a listening condition to assess the monaural performance of the contralateral ear. Interference of the cochlear implant on the performance of the contralateral ear can be evaluated by comparing the contralateral ear only condition to the cochlear implant + contralateral ear conditions when tested at 0° azimuth. This will be done at the 1 and 2 year test intervals only. Additionally, we will review the subjective benefit via the subjective questionnaires. If interference is found to impact speech perception and subjective benefit, the participant may elect to discontinue use of the cochlear implant and would still have access to currently approved technologies for UHL
 - ii) Magnet strength will be assessed at each interval to ensure comfort at the coil site.
 - iii) Reports of pain from the external speech processor placement will be addressed by different wearing options (i.e. moleskin between the external speech processor and the participant's ear, or different battery-wearing options to lighten weight on the pinna).
 - iv) Mapping will be conducted at each post-initial activation interval to improve audibility and comfort of the sound quality from electric stimulation.
 - v) The MED-EL cochlear implant has MRI limitations*. Participants may have CT scans or x-ray imaging postoperatively when warranted.

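### Sections 7, 8 and 9 name three different comparators for one effectiveness claim, and none is said to govern

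*Combined protocol and SAP*

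**What the plan says.** The comparator appears in four places.

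- **Background, last paragraph before section 2.** The goal is improvement "with a cochlear implant as compared to an unaided listening condition".
- **Section 9.b.i, primary effectiveness endpoint.** Speech perception, localization and/or subjective report are compared "when the cochlear implant is on versus the preoperative unaided condition".
- **Section 8.b.i and 8.b.ii, analysis.** For speech: "Comparison of aided speech perception performance to the baseline condition (either unaided or aided with hearing aid, depending on the participants residual hearing". For localization: "Comparison of localization abilities to the baseline condition (either unaided or aided with hearing aid, depending on the participant's residual hearing". The test is a repeated-measures ANOVA at p ≤ 0.05.
- **Section 7.a.i, proposed claims.** Improvement is to be shown "in an aided (cochlear implant on) versus an unaided (cochlear implant off) condition".

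Two other passages bear on whether these comparators are interchangeable. Inclusion criterion 7 requires "Aided word recognition in the ear to be implanted of 30% or less as measured with CNC words (50-word list", so a fitted hearing aid may give a non-zero score. Section 10.c.i says that, in a child with residual hearing, "surgical placement of a cochlear implant will result in a loss of this hearing".

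**The concern.** These are three conditions, not three names for one. A child with aidable hearing may score higher with a hearing aid than without it. Processor off after surgery is not the preoperative unaided ear either, because by the protocol's own account the residual hearing has gone, yet section 7 calls it unaided.

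Nothing ranks the three sections. No residual-hearing threshold decides which child gets which baseline under section 8, and no analysis by baseline type is planned. Two analysts following different sections could report different gains from the same data. Under section 8 the allocation of baselines could also be settled after scores are known. At stake is what the primary effectiveness result means: benefit over no device, benefit over a mixture of no device and a hearing aid, or benefit of switching the processor on.

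**Working it through.** **The plan's own figure.** There is no planned gain, SD or power to reproduce. The only planning figures are 20 children and about 20% dropout, which leave 20 × (1 − 0.20) = 16. The sample size is not in dispute here.

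**CNC in quiet: section 8 against section 9.** For each child let P be the postoperative implant score, U the preoperative unaided score and A the preoperative aided score.

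- Section 9 mean gain = mean(P − U).
- Section 8 mean gain = mean(P − B), where B = A for a share f of children and B = U for the rest.
- Section 9 gain minus section 8 gain = mean(B − U) = f × d, where d is the mean of A − U among children given the aided baseline.

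The documents give neither f nor d. Criterion 7 caps A at 30% and U cannot be below 0%, so no child's difference exceeds 30 points. I assume that A is not below U on average. The gap, in CNC percentage points, is then:

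| | f = 0.25 | f = 0.50 | f = 0.75 |
|---|---|---|---|
| d = 10 | 2.5 | 5.0 | 7.5 |
| d = 20 | 5.0 | 10.0 | 15.0 |
| d = 30 (all aided children at the cap, U = 0%) | 7.5 | 15.0 | 22.5 |

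Illustration with assumed scores P = 50, U = 5, A = 20 and f = 0.5: the gain is 50 − 5 = 45 points under section 9 and 45 − 0.5 × 15 = 37.5 under section 8. Against the hearing aid for every child it would be 50 − 20 = 30.

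Reclassifying one child among 16 moves the section 8 mean by d/16, which is 20/16 = 1.25 points at d = 20.

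**Which preoperative scores exist for CNC.** The candidacy evaluation (6.c.i) lists both unaided CNC and aided CNC in the affected ear. The preoperative evaluation, due within 6 months of surgery, lists unaided CNC only. Either baseline could therefore be applied to every child, but only the unaided score has a stated time window.

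**Localization and speech in noise.** The opening of 6.d mentions a preoperative interval for the battery in general. The specific entries do not: 6.d.v puts localization at 3, 9, 18 and 24 months after activation, processor on and off, and 6.d.iv puts BKB-SIN at 6, 12 and 24 months, on and off. Neither test appears in the candidacy or preoperative lists in 6.c. On the visible schedule, the preoperative localization baselines in 8.b.ii and 9.b.i cannot be computed; only the processor-off comparison can.

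**The case against.** **Single-subject design.** Section 8.b lets each child serve as his or her own control because outcomes vary, and a child-specific baseline (the best condition before surgery) fits that. Pooling of two baselines into one mean is an inference from the ANOVA; no group CNC gain is defined. That stands as a caution. But even child by child, sections 8 and 9 give different gains to anyone whose aided and unaided scores differ, and the selection rule is missing either way.

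**A reader might infer a very large distortion.** The 22.5-point cell needs three-quarters of the children to be aidable, all of them at the eligibility cap, with unaided scores of 0%. The documents point lower: section 10.c.i describes little or no functional residual hearing in the ear to be implanted.

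**A reader might infer that the unaided comparison is wrong and that the aided score should be primary.** The documents do not support this. The background and section 9 both ask an unaided question, and an unaided baseline answers it. The aided score also has weaknesses as a baseline:

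- It is the eligibility variable, so regression to the mean would favour the implant. One 50-word list at 30% has a binomial standard error of √(0.3 × 0.7 / 50) = 0.065, or about 6.5 points.
- It is listed only at candidacy.
- It is taken in sound field at 60 dB SPL, whereas postoperative CNC uses direct input at a comfortable level (6.d.iii).

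The hearing-aid trial is also conditional in criterion 6 and section 11 but unconditional in section 10.c.i; those passages must be reconciled.

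**Processor off.** The off conditions apply to binaural noise and localization tests. With contralateral thresholds of 25 dB HL or better and an implanted-ear average of 70 dB HL or worse, loss of residual hearing may change those scores little. That stands: the label is inaccurate, but no material bias is shown.

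**Feasibility study.** Both CNC scores are scheduled, so both contrasts could be reported, and no changed significance conclusion has been shown. This limits the severity but does not resolve which contrast is primary.

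**Conclusion.** The concern holds as a conflict between operative sections: the analysis in section 8 does not estimate the endpoint in section 9, section 7 adds a third comparator, and none is given precedence. For CNC in quiet the sections differ by f × d: 2.5 to 15 points for assumed f of 0.25 to 0.75 and d of 10 to 20, more only if aided children sit near the 30% cap, and nothing if f or d is zero. Section 9 gives the larger gain provided that aided scores are not below unaided ones.

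For localization, a preoperative comparison cannot be computed from the visible schedule. That part would fall if the Appendix A chart, which was not available, includes a preoperative localization test.

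The textual conflict is certain; its numerical size is illustrative. This should be fixed, but it does not show that the trial would reach a wrong conclusion.

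**What to change.** - In 8.b.i and 8.b.ii, delete the clause that makes the baseline depend on residual hearing. Name one comparator per measure, apply it to every child, and use the same words in sections 7, 8 and 9.
- **CNC in quiet:** align 8.b.i with the primary endpoint, the preoperative unaided score. Prespecify the gain over the aided candidacy score, for all children, as a separate contrast, so that benefit over a hearing aid is not confused with benefit over no device. State beside it that the aided score is also the eligibility score, with the attendant risk of regression to the mean, and that it was obtained in sound field at 60 dB SPL rather than by direct input.
- **Localization and BKB-SIN:** call the comparator *processor off after implantation*, not unaided or preoperative, in 7.a.i, 8.b.ii and 9.b.i, and limit the claim to that.

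The cost is wording in three sections and one extra contrast. No new testing is needed. The downside for the sponsor is that the gain shown against the hearing aid will be smaller wherever the aid helped.

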- (d) Assessment of hearing in contralateral ear
- (e) Mapping of the external speech processor

(7) Nine-Months Post-Initial Activation

- (a) Localization assessment
- (b) Parental questionnaires - anchored to prior questionnaires
- (c) Speech perception with the cochlear implant via direct input to processor
- (d) Mapping of the external speech processor

(8) Twelve-Months Post-Initial Activation

- (a) Hearing in noise assessment
- (b) Parental questionnaires - anchored to prior questionnaires
- (c) Speech perception with the cochlear implant via direct input to processor

- (d) Mapping of the external speech processor
- (e) Assessment of hearing in contralateral ear
- (f) Speech-Language evaluation

(9) Eighteen Months Post-Initial Activation

- (a) Localization assessment
- (b) Parental questionnaires - anchored to prior questionnaires
- (c) Speech perception assessed with the cochlear implant via direct input to processor
- (d) Mapping of the external speech processor

(10) Twenty-four Months Post-Initial Activation

- (a) Localization assessment
- (b) Hearing in noise assessment
- (c) Parental questionnaires - anchored to prior questionnaires
- (d) Speech perception with the cochlear implant via direct input to processor
- (e) Mapping of the external speech processor
- (f) Assessment of hearing in contralateral ear
- (g) Speech-language evaluation

d) Test Battery

The following test battery will be completed at various assessment intervals (preoperative, and at 3, 6, 9, 12, 18, and 24 months postoperatively) as defined in 6.iv. All assessment and mapping will be conducted at the Children's Cochlear Implant Center at UNC or at the Carolina Crossing research lab by board-certified audiologists.

i) Hearing Assessment

- (1) Air-conduction thresholds in both ears
 - (a) Air-conduction assessed with insert phones
 - (b) Assess bone-conduction thresholds if there is a PTA shift of >15 dB as compared to the previous interval
- (2) Aided thresholds with the external speech processor on will be measured using warble tones
 - (a) Frequencies assessed: 250-8000 Hz
 - (b) Masking presented to the contralateral ear (Turner, 2004).

ii) Tympanometry for each ear

iii) Speech Perception Measures in Quiet in ear of implant

- (1) Recorded materials will be presented at a comfortable listening level via direct input
- (2) Speech perception materials will be presented in a hierarchy, with advancement to the next test contingent on performance on the previous test

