 - iii) Serious Adverse Event: Serious injury means an injury or illness that: 1) is life-threatening, 2) results in permanent impairment of a body function or permanent damage to a body structure, or 2) necessitates medical or surgical intervention to preclude permanent impairment to a body function or permanent damage to a body structure.

- (1) Permanent means an irreversible impairment or damage to a body structure or function, excluding trivial impairment or damage.
- (2) Revision cochlear implantation will be considered a serious anticipated adverse event.

b) Reporting adverse events

- i) All adverse events will be reviewed by the PI during the preparation of the annual reports to the FDA and UNC IRB. Combined adverse events will be listed in an excel spreadsheet. Frequent adverse events will be discussed with co-investigators.
- ii) Anticipated events will be reported to the FDA in the annual report
- iii) Unanticipated events will be reported to the FDA and UNC IRB within 10 days of the investigator becoming aware of the event, as required by 21CFR 812.150.

13) Monitoring

- a) Participants will be monitored on a case-by-case basis for ongoing or unanticipated medical complications. Adverse events will be tracked on a case-by-case basis and recorded in study binders at the time of occurrence and followed up at resolution. Any adverse event will be reported to the UNC IRB. Should there be concern for the safety of participants because of their participation in the study by the investigators or the UNC IRB, the study would be halted at least temporarily and a detailed discussion with the investigators and UNC IRB would be undertaken to evaluate the viability of the study.
- b) Participants can withdraw from the study at any time and for any reason by notifying the Primary or Co-Investigators. If the investigator identifies the need to withdraw a participant from the study for any reason, this will be discussed in person during a scheduled evaluation. Participants may also be withdrawn if residual hearing changes in the contralateral (better hearing ear) to a moderate hearing loss or worse. In either scenario, the participant will continue to receive care irrespective of their participation in the study. Reasons for withdrawal from the study will be documented in the clinical visits and characterized based on the subjective reports from the child and family, performance on test measures, and the use of datalogging from the speech processor.

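### Section 13.b lets a fall in better-ear hearing end a child's study participation, and no section continues study data collection afterwards

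*Combined protocol and SAP*

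**What the plan says.** Section 13.b (Monitoring) gives a discretionary rule: "Participants may also be withdrawn if residual hearing changes in the contralateral (better hearing ear) to a moderate hearing loss or worse". It then says that "the participant will continue to receive care irrespective of their participation in the study", and "Reasons for withdrawal from the study will be documented in the clinical visits".

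The better ear must have thresholds of 25 dB HL or less at entry (section 6.b.i). In the visit schedule (section 6.c.iv), "Assessment of hearing in contralateral ear" is listed at 6, 12 and 24 months after activation. Section 5.c sets each child's endpoint at 24 months.

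On safety, section 9.a states: "The primary safety endpoint is the evaluation of Adverse Events". Section 13.a adds "Adverse events will be tracked on a case-by-case basis and recorded in study binders at the time of occurrence and followed up at resolution" and "Any adverse event will be reported to the UNC IRB". Section 8.a promises a descriptive summary of the "frequency of major and minor complications/adverse events", with no denominator or analysis set. Section 8.b analyses effectiveness by repeated-measures ANOVA, with each child as his or her own control, and gives no missing-data rule.

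**The concern.** Every child enters with one normal ear, so the hearing in that ear is an obvious safety outcome, and the plan schedules its measurement. Section 13.b makes a bad value of the same measurement a permitted reason to leave the study. If the rule is used, the observations that would show whether the change was temporary, stable or progressive are no longer secured as study data. The later visits would then be attended more by children whose better ear stayed good.

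The 24-month effectiveness results face the same selection. Whether a child contributes can depend on a post-implant measurement and on an investigator's choice for which no criteria are given. Missingness of this kind is informative whatever caused the hearing change.

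**Working it through.** **1. Is the change captured before the child leaves?** The rule applies only after a change has been found. If that change is classed as an adverse event, sections 12.b and 13.a have it recorded, listed and reported, and section 8.a counts it. The classification is not assured. The risk lists in section 10 name loss of residual hearing, without saying which ear, and interference of implant sound with the better ear. Neither expressly names a threshold decline in the better ear. Section 8 plans no analysis of better-ear thresholds that would show the change regardless of classification.

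**2. Is anything collected after the child leaves?** Section 13.b promises care and a documented reason. Section 10.c describes otologist reviews at 5 weeks, 6 months and 12 months as standard of care. No section says that such visits supply study data for a withdrawn child, or that audiometry, questionnaires or adverse-event collection go on. Section 13.a follows events up at resolution, and a permanent loss has none. Section 12.a counts permanent impairment of a body function as serious, and establishing permanence takes the later measurements that withdrawal may remove.

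**3. Follow-up lost, by time of exit.** Inputs: checks at 6, 12 and 24 months (section 6.c.iv) and the 24-month endpoint (section 5.c).

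| Exit at | Months lost | Share of 24 months |
|---|---|---|
| 6 months | 24 − 6 = 18 | 18/24 = 75% |
| 12 months | 24 − 12 = 12 | 12/24 = 50% |
| 24 months | 0 | 0% |

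**4. Weight of one child.** The plan's sample size is 20, with about 20% allowed for dropout (section 8). No power, effect size or SD is given, so 20 cannot be reproduced from a power formula. The allowance implies 20 × (1 − 0.20) = 16 completers, a figure the plan does not itself state. One child is 1/20 = 5% of those enrolled, or 1/16 = 6.25% of 16.

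**5. Illustration, assuming exactly one affected child** (Clopper-Pearson 95% limits; for zero events the upper limit is 1 − 0.025^(1/n)):

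- child kept: 1/20 = 5.0%, interval 0.1% to 24.9%;
- child left out of numerator and denominator: 0/19 = 0%, upper limit 1 − 0.025^(1/19) = 17.6%.

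**6. How likely is at least one case?** The documents give no event rate. The chance among 20 children is 1 − (1 − p)^20. For assumed p of 1%, 2%, 5% and 10% it is 18%, 33%, 64% and 88%.

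**The case against.** The strongest reply is that the child does not leave the safety data. A reader might infer from section 13.b that the case disappears, but the documents do not support that. Events are recorded when they occur, all go to the IRB, the reason for withdrawal is documented, and nothing says that a withdrawn child's earlier data are deleted or the child dropped from a denominator. This stands for the triggering event, provided it is classed as an adverse event. It does not cover later follow-up.

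Three other stronger readings also fail:

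- **That this is the gravest harm in the study.** Section 12 covers death and life-threatening events, and section 10 lists CSF leak and facial nerve injury. A potentially serious harm is as far as the text goes.
- **That the implant causes the loss.** The better ear is not operated on. Children with an enlarged vestibular aqueduct or IP2 are eligible, so other causes are possible. The missing-data problem does not depend on cause.
- **That these exits come on top of the 20% dropout allowance.** They may fall within it.

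It is also fair that the rule is permissive, that the 75% loss applies only to a 6-month exit, and that loss of a child's earlier effectiveness data would need complete-case handling in the ANOVA, which the plan does not specify.

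Finally, a child with a moderate loss in the better ear no longer has the condition under study, so processor-on versus processor-off results change meaning. That is a sound reason to flag those results or analyse them separately. It is not a reason to stop collecting safety data.

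The absence of analysis sets and a missing-data rule affects every withdrawal. What is particular here is an explicit rule that ties exit to a measured outcome.

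**Conclusion.** The point holds as a gap in data collection and analysis, and the plan should be changed. As written, it permits withdrawal on a post-implant outcome and provides no study follow-up afterwards. Later better-ear, adverse-event and effectiveness data may therefore be missing in an outcome-dependent way.

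The size is conditional. One affected child moves the observed rate between 5.0% and 0% only if that child is left out, which the plan neither states nor rules out. The lost follow-up is 18 or 12 of 24 months only if the child exits at the 6- or 12-month visit. Without an event rate, the expected effect cannot be stated. No judgement is made on clinical management or device use.

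**What to change.** Limit the change to data collection and analysis.

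1. Amend section 13.b so that a better-ear change does not by itself end study follow-up. With consent, continue the scheduled audiometry, adverse-event collection and questionnaires to 24 months.
2. Add to section 8.a a table of each child's better-ear PTA change from the preoperative value at 6, 12 and 24 months, with all implanted children in the denominator. The change is then reported however it is classified.
3. Flag processor-on and processor-off results obtained after the change, and show the effectiveness analysis with and without them.

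The cost is a few sentences of protocol wording, since the visits are already scheduled. The downside is a small number of flagged visits from children who no longer fit the unilateral-loss definition.
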